## 6.4. Specimen Collection

Urine test results will be collected from female participants to determine whether or not they are pregnant before study enrollment (Week1) and every 5 to 6 weeks thereafter until study completion. There will be no storage of collected urine. The urine samples and test sticks will be disposed of immediately after a successful pregnancy test has been conducted and recorded by study staff.

## 7.0 Expected Risks/Benefits

**Potential Benefits.** Participants will receive brief behavioral counseling and the SREC to help them reduce their combustible tobacco use which has the potential for improvements to their health as well as money saved from purchasing cigarettes. Participants will receive monetary payment for completion of their assessments through a university issued check. Participation in the study ultimately will help other smokers in the future by improving our knowledge of how e-cigarettes might be used to help smokers reduce or stop smoking cigarettes.

**Protections Against Risks.** We believe that the risk of participation is minimal, and any potential risks from the use of SREC are likely to be considerably less than those that result from cigarette smoking. In general, there have been extremely few documented risks associated with non-THC, nicotine containing e-cigarette use among current smokers. Participants will be informed about EVALI and provided with CDC recommendations on e-cigarette use during the consent process and throughout the trial. Participants will also be informed of potential adverse effects of reducing their smoking and using the SREC, including experiencing withdrawal symptoms. Over the course of our previous research studies, we have developed extensive procedures and protocols for minimizing the risks of participation.

**Participant Training for EMA.** Clinical Staff conduct careful training procedures with participants at the beginning of each EMA week. This training is focused on appropriate use of the EMA device, including when to “suspend” the EMA program so that it will not randomly prompt participants during times when it might be dangerous to respond to interviews (e.g., driving). In addition, staff will role-play with participants on how to deal with potentially awkward situations in order to complete random prompts or event record their cigarette and SREC use. The trainer will help participants anticipate and problem-solve any concerns they have about using the device in their everyday lives for the 7-day monitoring period.

**Distress.** We believe the risk of experiencing distress as a direct result of participating in the proposed research is minimal given the nature of the measures that we will be collecting. Participants may experience some withdrawal distress as they switch to SREC and reduce their cigarette smoking, but we believe that this is minimal. In our 20 years of conducting similar studies with a variety of high-risk populations (e.g., adolescents, young adults, disadvantaged) we have not had participant complaints about the procedures causing any distress; rather participants usually find the procedures interesting. However, we are prepared to manage this situation, should it occur. [name] are clinical psychologists and will provide training for staff on identifying and responding to emotional distress in a research participant. Staff will be required to notify [name] immediately upon discovery of any problems or distress with a participant.

**Confidentiality.** Confidentiality of all data we collect are assured by using a unique numerical identifier for each participant. The master list of name and identifier match is restricted to only personnel who require the match for essential study tasks. The list will reside in a password protected file kept separate from all other data and study materials. Materials that contain individuals' names or other important contact information (e.g., mailing address, phone, email) will also be restricted and password protected. Identifying information and data are not stored together. The EMA program is password protected and accessing and downloading the data requires a custom download program that can only be accessed by authorized study staff. If a participant were to lose a phone, no one else could access data stored by the EMA program. We have developed extensive procedures and protocols in our current and previous EMA studies with no accidental disclosure or adverse consequences to study participants. We believe that staff training is crucial to ensuring confidentiality. Staff will participate in UIC's human subjects protections training, along with specific, project-focused training and frequent reviews with [name] and [name] (Senior Data Manager) to ensure staff understanding and compliance with project protocols.

**Risks around the e-cigarette (SREC).** We believe that the risks of adult regular smokers using SREC are minimal, given the prevalence of use of e-cigarettes and the consensus that they are far less harmful than conventional cigarettes. According to the recent (2018) National Academy of Science report, "The evidence about harm reduction suggests that across a range of studies and outcomes, e-cigarettes pose less risk to an individual than combustible tobacco cigarettes." (p. S-8). Nevertheless, we will discuss with participants that all tobacco use may present some harm, and that no tobacco use is healthy. We will provide an information sheet to participants each time we dispense the SREC to them. At the enrollment visit (during the consent process) and at the end-of-treatment visit, we will tell participants that the long-term safety and health effects of using e-cigarettes is unknown. We will also discuss in-person and include on the information sheet that the SREC device contains nicotine, which can be hazardous to children and pets if ingested. We plan to discuss plans for storing the device and refills in their homes. We will also provide education to participants on the symptoms of nicotine toxicity (nausea and vomiting) and the signs and symptoms of developing an EVALI so that they are aware and can reduce their exposure if they experience these symptoms. Additionally, the SREC packaging of the battery and each pod is clearly marked "for investigational purposes only." We also will instruct participants about the risks associated with using nicotine products while pregnant and/or nursing, and study staff will record results from pregnancy tests taken during study visits for women of childbearing age throughout participation.

Given that the risks involved in this proposed research are relatively minimal, the benefits of participating greatly outweigh the risks.

## **8.0 Data Collection and Management Procedures**

The data for this study are provided directly from the participant and are collected solely for research purposes. Data will come from: the online and telephone screening surveys, computer administered questionnaires, online daily use surveys, health assessments (pregnancy test results, expired air CO, height, weight, blood pressure, pulse), semi-structured debriefing interviews, and real-time EMA. Aside from the EMA data collection, all other data will be collected using REDCap and maintained on the secure IHRP server. Participants will complete questionnaires for the in-person visits on a tablet using REDCap to reduce missing data or errors.

The questionnaires completed by participants at all study visits as well as the daily use surveys will be programmed into REDCap (baseline and week 14/End of Treatment) or REDCap (all brief questionnaires at all remaining study visits) for data collection on a tablet during the in-person visits. The daily use surveys will be programmed within REDCap, a secure web-based application for data management that can be programmed for daily email reminders and links.

The health measures (CO, pregnancy test results, height, weight, blood pressure, and pulse) will be recorded on a hard-copy forms that only contains the study ID. This data will be entered into REDCap shortly after each study visit by research staff. The hard copy forms will be filed in a locked cabinet in a locked office until for four years after the study is completed and then shredded.

The EMA data collection (i.e., smartphone and app) will be password protected so only the participant has the ability to enter and record data. All EMA data reside on the app until the participant returns to our study office at the end of their EMA week. We then download the data to our secure server and wipe the app clean of all data. All entries will be time and date stamped, and the app will record response time to a prompt, missed prompts, wake and sleep times, and app "suspensions" and the reasons. Participants may "suspend" the app for up to three hours when responding would be impractical (e.g., while driving; at movies). The app programming prevents skipping items or entering out-of-range values. Once the interviews are recorded, only study personnel with an administrative password will be able to access the data stored on the device, from which it will be downloaded to a laptop for debriefing interview purposes, and then transferred to the secure IHRP server. The laptop used in the debriefing interview will never be connected to the internet and will never leave our research office while there is data on it. Immediately following the debriefing interview, the laptop will be connected to the IHRP server to transfer the data, and then the data will be deleted from the laptop.

Managing EMA data includes data collection, debriefing, documentation, extraction, aggregation, and cleaning. During the EMA week, data are stored on the app on the study-provided smartphone. At post-EMA debriefing at week's end, we collect the phone, download the data (for storage on a secure server), and print a debriefing report. The report contains all the participant's interactions with the app, helps gauge compliance,

and establishes positive reinforcement for future waves. The report documents problems encountered (e.g., erroneous entries). These data are corrected after data aggregation. All ASCII files are aggregated using MS-DOS batch commands; the resulting aggregated ASCII is read into SAS and formatted.

**Data Management.** [name] will develop the centralized databases that will be used to collect, process, and manage data relating to the eligibility screening, enrollment, randomization, intervention delivery, and follow-up. Data processing will include: de-identification of the online screener and implementation of the unique ID for each participant, and transferring the data from the smartphones to the IHRP secure server, followed by subsequent cleaning, documentation, and construction of master files for all of the data collection instruments. The datafiles will be maintained on the IHRP secure network that allows investigators and key research personnel access to data files and accompanying documentation. These files will be made available to approved investigators on the project.

REDCap has sophisticated user rights controls that allow some users access to certain REDCap functions but not others (e.g., allowing data exports or not, viewing summary statistics and charts, adding or editing records, etc.). It also supports a complex longitudinal study structure to allow for form reuse and a univariate or “stacked” data structure. We will leverage the many built-in features in REDCap (e.g., data type validation, valid values/range rules, required responses) and extensive data rules that allow for complex real-time quality control checks (e.g., of missing values, out of range values, logic comparisons, cross form/event consistency).

Every other week, a quality control report will be generated to quantify the accuracy and timeliness of data collection and entry, identify missing data, and examine frequencies to detect unanticipated problems or biases. Quantitative data stored in REDCap will be exported directly from the REDCap database to the Switch to SREC’s storage folder on the IHRP network for processing. Research staff responsible for analyzing data, both at UIC and UofC, will only have access to processed and deidentified data files. They do not have access to raw responses from the REDCap database, nor can they access participant names or other contact information. Data will be shared with [name] at UofC using Virtual Private Network (VPN) access to the IHRP server.

Syntax will be used for constructing the planned dataset and for running all analyses. This will allow the investigators to review each step of the analytic process for errors and to ensure the appropriate analyses have been done (and can be repeated with the same results). These syntax files will be saved along with the output files and each corresponding manuscript so that it can be used in responding to reviewers, and it will be available upon request for sharing.

## 9.0 Data Analysis

**Aim 1. Examine whether conventional cigarette smokers can significantly reduce their combustible cigarette use by switching to SREC.** We will have assessments of the amount of SREC and combustible cigarettes used every week for 12 weeks. SREC/e-cigarette use per day is captured by the total number of e-cigarette episodes defined as about 15 puffs or a period lasting about 10 minutes. Both of these outcomes will be modeled as count data (average # cigs/day and SREC episodes/day for each week) using a mixed-effects Poisson regression model (or Negative Binomial model if the Poisson assumption of equality of mean and variance is not met). In these analyses, we will examine primarily linear and curvilinear changes across time using orthogonal polynomial transforms, in order to assess the independent effects of these two types of trends, which will be treated as random effects to allow heterogeneity across subjects in the time trends. These time trend analyses will allow us to investigate the **sustainability of reductions in cigarette use and changes in SREC use**. In addition to the effect(s) of time, the main independent variable is group (usual flavor or flavor choice). Although we expect the group effect to be consistent across the 12 weeks, we will test whether the group effect varies across time (i.e., group by time interaction). For example, it may be likely that differences between the groups increase over time if the usual flavor group more rapidly relapses back to smoking cigarettes and gives up on their SREC. Our primary endpoint will be the model-based estimate of the group difference at the final 12-week timepoint (study week 14). We will also consider the proportion of participants who achieve total abstinence from combustible cigarettes at the end of the 12-week trial (defined as no cigarette smoking in the past 7 days and confirmed by CO < 3 ppm; see power section). Although our primary endpoint is the end of the 12 weeks of treatment, (week 14) we will also evaluate effects at the one-month follow-up. In terms of these primary outcomes, we will further examine the degree to which

group differences are moderated by gender, baseline menthol cigarette use (not SREC flavor), and nicotine dependence level, and also examine the degree to which baseline characteristics might predict success on these outcomes. We will use descriptive statistics to report the frequency of flavor choice, how that varies over time, by condition, and by level of reduction.

We will also be weighing all returned SREC pods and will also be able to develop a measure of SREC use per week based on SREC pod weight.

**Aim 2. Examine whether reductions in conventional cigarette use and uptake of SREC are associated with changes in health and biomarker variables.** Smokers may vary in how completely they substitute SREC for their conventional cigarettes. Thus, for each participant, we will have, on a weekly basis, the number of cigarettes smoked and the number of SREC episodes or returned SREC pod weights. As indicated above, these will be modeled using mixed models for counts, which yield empirical Bayes estimates for each subject of their change across time in cigarette and SREC usage. We will examine how these change in usage estimates are associated with changes in the following variables: 1) CO level; 2) blood pressure; 3) heart rate; 4) weight (assessed baseline and at end); 5) self-report of respiratory symptoms (baseline and at end); and 6) nicotine dependence (assessed at baseline and end). For each of these continuous outcomes, we will use linear mixed models with effects of time and group (usual flavor or free choice), and group by time interaction if significant. To these models, we will add in the empirical Bayes estimates of cigarette and SREC change (obtained from the stage 1 mixed models for counts) and specifically examine the change by time interactions (and change by group by time if the group by time interaction is significant). As the empirical Bayes estimates from the stage 1 analyses have uncertainty attached to them, we will use the resampling approach advocated by Tsonka et al for using empirical Bayes estimates from a first stage analysis as covariates in a second stage model.

**Aim 3: Examine smokers' subjective responses to SREC in real time, and whether these responses are associated with cigarette reduction.** Levels of satisfaction, pleasure, mood change following use, and withdrawal symptoms will be assessed via EMA during the second week of SREC use. Level of satisfaction, pleasure, and mood will be assessed following each use of SREC (event report), and withdrawal symptoms will be assessed both during random times and following SREC use. We will also descriptively examine how the SREC flavor may be associated with adherence and overall level of subjective responses. We will use linear mixed models to compare groups in terms of the EMA subjective reports and withdrawal symptoms. Also, using the empirical Bayes estimates from these linear mixed models of EMA-reported subjective experience and withdrawal, we will examine whether these predict longitudinal changes in cigarette use over the following weeks, which will be modeled using a Poisson mixed model including effects of group, time (and group by time if significant). We will specifically examine the effects of satisfaction and withdrawal on cigarette use, both as main effects and as interactions with time if significant. Again, we will follow the resampling approach to account for the uncertainty of the empirical Bayes estimates.

**Aim 4. Examine how patterns of use (e.g., contexts, timing) and subjective experience with SREC, differ from conventional cigarette use, and whether differences are associated with success in switching to SREC (giving up or reducing combustible and using SREC).** We will have baseline EMA data on smoking events and random time sampling of urges, mood, satisfaction with smoking, as well as context. Then we will have a week of EMA data on the second week of the instructed switch to SREC. We will compare EMA data during baseline to the SREC switch week on the following within subject factors: context of use (alone, with others; location – home; work; in public; presence of other smokers; time of day (e.g., first cigarette of the day); mood prior to use; mood after use; urge prior to use and at random time; satisfaction after use). We will use three-level (observations within weeks within subjects) linear mixed models for continuous outcomes (mood), logistic mixed models for binary outcomes (context), and survival mixed models for time to an event (first cigarette of the day). The main independent variable will be the indicator of EMA week (baseline/switch week) to test whether the outcomes vary by EMA week. We will also control for group (usual flavor/flavor choice) and examine whether the effect of EMA week varies by group. Analyses will also include sex and prior menthol use as covariates.

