Adverse Events (e.g., throat irritation, nausea)			x	X	x	x	x	x	x	x	x	x	x	x		

A. A **Comprehensive questionnaire** (baseline and 14-Week End of Treatment visits) will be completed in-person to assess key constructs [e.g., sociodemographics, tobacco and nicotine use (history, dependence, attitudes, motivations, intentions, perceived harm), tobacco environment, cessation history and intentions, and other substance use]. Each questionnaire will take approximately 30 - 40 minutes to complete. Shorter **brief surveys** (5-7 minutes to complete) will be completed at weeks 2, 3, 4, 6, 8, and 11. These measures serve as important descriptors of our sample, serve as covariates or moderators in our analyses, and serve as predictors of success in reducing cigarettes and switching to SREC over time.

B. A **daily use survey** completed online via REDCap from an emailed or texted survey link starting at the week 2 visit through the week 14 visit (over the 12 treatment weeks) to assess the use of cigarettes, SREC, and any other e-cigarette/nicotine vaporizer. Each of these surveys will take about 1 minute to complete. This brief survey will serve as an indicator of change in patterns of use as well as a way for the Clinical Interviewer Staff to track progress with cigarette reduction and to monitor nicotine exposure during the treatment phase. Daily surveys ask about the number of cigarettes smoked and the number of SREC or other e-cigarette episodes on the previous day (an episode is defined as 15 puffs or a period lasting about 10 mins). We also ask if the participant finished a pod on the previous day.

C. **Two, week-long waves of EMA data collection** using a **study provided smartphone**, the first wave will take place immediately following completion of the baseline questionnaire (week 1 visit through week 2 visit), and the second wave will take place starting at the week 3 visit through the week 4 visit. The first week of EMA provides the baseline comparison with combustible cigarettes to the second EMA wave when participants will have one week of experience with using the SREC and some practice cutting down on their cigarette smoking. Each EMA wave will cover 7 consecutive days, ensuring both weekday and weekend sampling.

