## 12.0 Statistical Considerations

**Attrition and nonresponse.** Despite our efforts, some attrition and missing data are likely. The mixed model does allow missing data and provides valid results under the assumption of missing at random (MAR). MAR means that the missingness can be related to model covariates as well as observed values of the dependent variable and is sometimes termed "ignorable" missingness. As Molenberghs et. al. detail, MAR is a relatively weak and non-restrictive assumption about the missing data. Nonetheless, the possibility of non-ignorable missingness cannot be ruled out and so, as advocated by Molenberghs et. al., we will conduct sensitivity analyses using non-ignorable pattern-mixture and selection models to investigate the robustness of our conclusions across these different models for missing data. These sensitivity analyses apply to the both the longitudinal and EMA models that we have proposed. In particular, in the EMA context we will jointly model the outcomes and EMA prompt missingness, with random subject effects shared by both models. In this way, our model for the outcome will control for a person's propensity to miss EMA prompts.

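### Aim 1 models weekly averages per day as Poisson counts, which misstates the variance and ignores how many diary days were reported; the primary contrast is hardly touched, but the personal trends used in Aim 2 can suffer

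*Combined protocol and SAP*

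**What the plan says.** Under Aim 1 of Section 9.0, cigarettes and SREC episodes are treated alike: "Both of these outcomes will be modeled as count data (average # cigs/day and SREC episodes/day for each week"). The model is a mixed-effects Poisson regression, "or Negative Binomial model if the Poisson assumption of equality of mean and variance is not met". It has linear and curvilinear time trends, "which will be treated as random effects to allow heterogeneity across subjects in the time trends".

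The raw data are finer than that. Item B of Section 6.3 states: "Daily surveys ask about the number of cigarettes smoked and the number of SREC or other e-cigarette episodes on the previous day". A weekly value can therefore rest on anything from one to seven reports.

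Under Aim 2, Section 9.0 describes the data as "on a weekly basis, the number of cigarettes smoked and the number of SREC episodes or returned SREC pod weights", says they are modelled as set out for Aim 1, and relies on models "which yield empirical Bayes estimates for each subject of their change across time in cigarette and SREC usage". These estimates become covariates in the second-stage models. Resampling is planned because: "As the empirical Bayes estimates from the stage 1 analyses have uncertainty attached to them".

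Section 12.0 concedes: "Despite our efforts, some attrition and missing data are likely". Its remedies are a missing-at-random analysis with pattern-mixture and selection models as sensitivity analyses. Nowhere is there an offset, a weight or a minimum number of reported days per week.

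**The concern.** A Poisson model ties the variance of the outcome to its mean. That may suit a day's count or a week's total, but not an average, whose variance also depends on how many days went into it. Three things follow.

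- Comparing the variance of the averages with their mean is not a test of whether the underlying counts are Poisson.
- The Negative Binomial variance is never below the mean, so the fallback cannot represent an average whose conditional variance is below its mean.
- Neither distribution is told how many days were reported, so weeks of very different precision get equal weight.

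At stake are the split between within-person and between-person variation, and the individual trends computed from it. If within-person noise is overstated, personal trends are shrunk too far towards the group mean. Aim 2 uses those trends as its exposure variables. The resampling step takes its uncertainty from the same stage 1 model, so it does not correct a wrong conditional variance.

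**Working it through.** **Inputs.** Section 12.0 gives 54 per arm at the end, a rate ratio of .75 (8.2 vs 11, or 11.25 vs 15 cigarettes/day), power .8, and for Aim 2 r = .262 with n = 108. A two-tailed .05 level is stated for Aim 4 only and is assumed here. The documents do not give the daily dispersion φ, the between-day correlation ρ, the diary response rate or the random-effect variances; all values of these below are assumptions.

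**1. The plan's own figures.** With SE = √[φ(1/μ₁ + 1/μ₂)/54] and φ = 1:
- 11 vs 8.2: SE = √(0.2129/54) = 0.063, |log ratio| = 0.294, power 0.997.
- 15 vs 11.25: SE = √(0.1556/54) = 0.054, |log ratio| = 0.288, power 0.9997.

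Power of 0.80 needs φ of about 2.8 or 3.7. The plan states no dispersion, so its figure can be neither reproduced nor faulted. That φ also includes differences between people, so it does not supply the daily within-person φ needed below. The Aim 2 figure does reproduce: r = .262 with n = 108 gives 0.785 by Fisher z.

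**2. Variance of a d-day average.** Var = φμ[1 + (d − 1)ρ]/d, while the Poisson model assumes μ. Assumed over actual = d / {φ[1 + (d − 1)ρ]}:
- d = 7, φ = 1, ρ = 0: 7 (at μ = 11, 11 assumed against 11/7 = 1.57)
- d = 1, φ = 1: 1
- d = 7, φ = 2, ρ = 0: 3.5
- d = 7, φ = 3, ρ = 0: 2.3
- d = 7, φ = 7, ρ = 0: 1
- d = 7, φ = 3, ρ = 0.4: 7/(3 × 3.4) = 0.69, so the variance is now understated

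**3. Primary contrast at week 12**, averages against totals with a log(days) offset:
- Mean 11, φ = 1, seven days, intercept SD 0.5, slope SD 0.6: SE 0.112 vs 0.112; rejection under the null 0.076 vs 0.080; power at a ratio of .75 0.70 vs 0.69.
- Mean 2, φ = 1, 80% of diaries, intercept SD 0.7, slope SD 0.6: SE 0.151 vs 0.150.

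Between-person variation dominates. In the first case, if time runs from −0.5 to 0.5, it alone gives √[2(0.25 + 0.36 × 0.25)/54] = 0.112.

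**4. Personal trends.** Poisson mixed models, 54 per arm, 12 weeks, intercept SD 0.5, random linear slope only, 250 data sets per row. Each cell shows averages vs totals with offset.

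| Mean/day | Slope SD | φ | Days reported | Correlation with true slope | Slope MSE |
|---|---|---|---|---|---|
| 11 | 0.3 | 1 | 7 | 0.84 vs 0.93 | 0.048 vs 0.012 |
| 11 | 0.6 | 1 | 7 | 0.973 vs 0.978 | 0.035 vs 0.019 |
| 11 | 0.6 | 4 | about 60% | 0.86 vs 0.87 | 0.100 vs 0.106 |
| 3 | 0.3 | 1 | 7 | 0.07 vs 0.82 | 0.091 vs 0.031 |
| 3 | 0.6 | 1 | 7 | 0.89 vs 0.94 | 0.168 vs 0.046 |
| 3 | 0.3 | 4 | about 60% | 0.43 vs 0.46 | 0.087 vs 0.190 |
| 3 | 0.6 | 4 | about 60% | 0.68 vs 0.70 | 0.204 vs 0.268 |
| 3 | 0.6 | 7 | 7 | 0.75 vs 0.74 | 0.163 vs 0.269 |

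The φ = 4 rows fit step 2: about 60% of 7 is 4.2 days, and 4.2/4 = 1.05, so the averages happen to carry roughly the right variance.

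Further runs with SDs 0.7 and 0.6 and 80% response gave 0.94 vs 0.96 (mean 8.2, φ = 1), 0.87 vs 0.87 (mean 8.2, φ = 4) and 0.68 vs 0.67 (mean 2, φ = 4). At mean 2 with φ = 1, three separate runs gave 0.72 vs 0.88, 0.81 vs 0.87 and 0.87 vs 0.90. Time coding may explain part of that spread, so only the direction is firm.

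**The case against.** The strongest reply is that this changes little. The primary contrast does not move. At the 8.2 to 15 cigarettes/day of the power section, with slope SD 0.6, the loss in trend accuracy is slight. The plan itself foresees overdispersion, and with overdispersed, correlated days the Negative Binomial adds variance in the right direction. The wording is also open to another reading: Aim 2 speaks of a weekly number of cigarettes and Section 12.0 of a rate, so a rate model may be what is meant.

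Much of this stands. The harm is conditional, and the primary result is not at risk. Three things remain. First, Aim 2 refers back to the Aim 1 model, whose text says average, so the ambiguity is itself a gap. Second, any match between assumed and actual variance is a coincidence of dispersion and diary response, and it shifts from week to week as the days reported change. Third, low counts are what the intervention seeks: Section 6.1 sets a goal of at least 75% reduction in the first week, which from 11 to 15 a day means 2.75 to 3.75 (0.25 × 11 and 0.25 × 15). That is the region where the loss can be large if days are near Poisson.

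A fair warning also applies to the remedy. Plain Poisson on totals is worse than averages for slope MSE in several overdispersed rows above, so an offset alone is not enough.

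**Conclusion.** The outcome as written is misspecified: the conditional variance is wrong, by an amount that depends on the days reported, and the stated check and fallback do not address it. The plan should be corrected, but as a matter for the variance components and the Aim 2 trends. The size runs from negligible (daily dispersion about 4, or means of 8 to 11 a day with large slope variance) to material (near-Poisson days with low counts or small slope variance). All of this rests on assumed dispersion, response and random-effect values, and on fits without the curvilinear random effect.

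Four stronger conclusions that a reader might draw are not supported:

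- **The primary test is compromised.** Its standard error is the same to within 0.001 in both comparisons.
- **The variance is wrong sevenfold.** Seven is the ceiling for overstatement and needs independent Poisson days with all seven reported.
- **Aim 2 power falls from 0.67 to 0.50.** This is a favourable-case illustration: 0.262 × 0.88 = 0.231 and 0.262 × 0.72 = 0.189, put through Fisher z with n = 108. At 8.2 a day the same method gives about 0.75 and 0.73, and with φ = 4 there is practically no difference. It also treats .262 as a correlation with the true trend, whereas Section 12.0 likens it to correlations observed in earlier studies, and it replaces the planned mixed models with a single correlation test.
- **Light smoking would be rounded to false abstinence.** The plan describes no rounding, and abstinence is a separate outcome confirmed by CO.

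**What to change.** In Section 9.0, Aim 1, define the outcome as the weekly total of cigarettes (and, separately, of SREC episodes) with log(number of days reported that week) as an offset; or model the daily counts, with days nested in weeks and weeks in persons. Assess overdispersion on those counts, conditional on the random effects, and where it is present include a term for it, such as a Negative Binomial distribution or an observation-level random effect. Use the same outcome definition in the stage 1 models of Aim 2 and in the Poisson model for cigarette use in Aim 3, so that the wording on averages, numbers and rates agrees.

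The cost is a few sentences in the analysis plan. The daily reports are already collected, so no procedure, visit or sample size changes.
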